When the investigator decides to extend the treatment interval from 16 to 20 weeks, the investigator has the option to plan for an inspection visit 4 weeks before the next treatment visit (i.e. 16 weeks after the last treatment visit) to assess DA. If the study eye has no DA at the inspection visit, the participant will not receive study treatment at the inspection visit but 4 weeks later. If the investigator observes DA in the study eye at the inspection visit, the participant will receive study treatment at this visit. The treatment interval will then be reduced by 4 weeks and the next study treatment visit will be planned 12 weeks after the inspection visit.

When the investigator decides to extend the treatment interval from 8 to 12 weeks, the investigator has the option to plan for an inspection visit 2 weeks before the next treatment visit (i.e. 10 weeks after the last treatment visit) to assess DA. If the study eye has no DA at the inspection visit, the participant will not receive study treatment at the inspection visit but 2 weeks later. If the investigator observes DA in the study eye at the inspection visit, the participant will receive study treatment at the inspection visit. The next treatment interval will be reduced to 8 weeks. The same optional inspection visit 2 weeks earlier than the next treatment visit will be offered, when the investigator decides to extend the treatment interval from 12 to 16 weeks. If the study eye has no DA at the inspection visit, the participant will not receive study treatment at the inspection visit but 2 weeks later. If DA is observed in the study eye at the inspection visit, the participant will receive study treatment at the inspection visit. The next treatment interval will be reduced to 12 weeks. If the patient requires a reduction of the treatment interval down to 4 weeks, the patient will receive an injection at the visit, but will be discontinued from further study treatment at the next visit.

Regardless of treatment administration, Week 52 and Week 56 visits are mandatory. Participants who will receive study treatment at an inspection visit may also have a study visit

at Week 54; for these participants, the Week 54 visit will take place in lieu of the visit at Week 52 (unless this visit is inspection visit), respectively.

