Proportion of participants with at least 16-weeks duration of last interval with no disease activity excluding participants with important protocol deviations	Sensitivity estimand 1.4	Proportion of participants in last interval with no disease activity that is at least 16-weeks intervals at Week 56, excluding participants with important protocol deviations as per PPS	PPS**	*Last interval with no disease activity up to Week 56	Two-sided 95% Confidence Interval of proportions. If there was disease activity, the last interval will be shortened by 4 weeks, down to a minimum of 4 weeks

Endpoint	Estimand	Estimand definition	Analysis set	Data included in analysis	Statistical methods (including missing data strategy)
Proportion of participants with at least 16-weeks duration of the last interval with no disease activity excluding participants with important protocol deviations either in the core study or in the extension study	Sensitivity estimand 1.5	Proportion of participants in last interval with no disease activity that is at least 16-weeks intervals, excluding participants with important protocol deviations either in the core or in the extension as per PPS	PPS**	*Last interval with no disease activity up to Week 56	Two-sided 95% Confidence Interval of proportions. If there was disease activity, the last interval will be shortened by 4 weeks, down to a minimum of 4 weeks

*: If the duration of the last interval falls within the following ranges of [q4w, q8w) or [q8w, q12w), [q12w, q16w), [q16w, q20w) or \geq q20w then the floor value of these ranges i.e. q4w, q8w, q12w, q16w, q20w, respectively, will be used for imputation.

** : Patients who take prohibited concomitant medication are already excluded from PPS as taking prohibited medication is considered a deviation with impact.

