2.1.1 General definitions

All the definitions, e.g. baseline, on-treatment period, are referring to the current extension study unless otherwise stated, e.g. baseline of the core study.

Study treatment is defined as brolocizumab 6 mg/0.05 mL.

Date of first administration of study treatment is defined as the first date when a non-zero dose of study treatment is administered and recorded on the case report form (CRF) dose administration page. The date of first administration of study treatment will also be referred to as start of study treatment.

Date of last administration of study treatment is defined as the last date when a non-zero dose of study treatment is administered and recorded on the CRF dose administration page. The last administration of study treatment will also be referred as end of treatment (EOT).

Study day will be calculated as:

- The date of the event (visit date, onset date of an event, assessment date etc.) – treatment start date + 1, if event is on or after the treatment start date;
- The date of the event (visit date, onset date of an event, assessment date etc.) – treatment start date, if event precedes the treatment start date.

Baseline/Day 1 is the end of study (EOS)/Week 64 of the core study.

On-treatment period is defined from Day 1 of the study to 30 days after the last administration of study treatment (i.e. EOT) or end of study (EOS), whichever is the latest.

Treatment interval is defined as the time period from one injection until the next injection. In this study, treatment intervals of q4w, q8w, q12w, q16w and q20w, meaning that there are 4, 8, 12, 16 and 20 weeks between 2 injections, are of special interest. The last (treatment) interval at Week X is referred to the last complete interval where injections at both ends of the interval have occurred on or before Week X. The last interval with/without disease activity is referred to the last interval with/without disease activity as observed at the end of the interval.

The first treatment is defined by the treatment interval of the core study. For example, a patient who started a 16-weeks interval at Week 56 of the core study will have the first treatment 8 weeks after the start of the extension study (i.e. 8 weeks after Week 64).

Participants will be assessed for eligibility based on inclusion and exclusion criteria for the extension study at the baseline visit.

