The study day will be displayed in data listings. All data from scheduled and unscheduled visits will be analyzed based on “Week XX” recorded in the CRF (except for baseline), unless otherwise stated.

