2.5.2 Statistical hypothesis, model, and method of analysis

The average change in BCVA from baseline of the extension study at Week 52 and Week 56 will be estimated by an analysis of variance (ANOVA) with baseline age categories, baseline BCVA categories and treatment arm in the core study included as fixed effects. The estimate of BCVA change will be accompanied by the 95% CI.

For the analysis of durability, the first step is to identify the last (treatment) interval with respect to Week 56 for each participant, i.e. the last interval for which injections have occurred at both ends of this interval before/at Week 56. If there is disease activity at the end of the last interval, then the last interval will be shortened by 4 weeks, down to a minimum of q4w. Subjects who do not receive any injection (or only one injection) of study drug in the extension study will be excluded from this analysis. In case of any treatment interruption or permanent study treatment discontinuation, the imputation techniques as per the estimand framework in [Section 2.5.3](#) will be considered. Then, the proportion of participants with last interval of q4w, q8w, q12w, q16w, and q20w will be specified. These proportions will be referred as the distribution of the last interval.

The distribution of the last interval with no disease activity up to Week 56 will be described based on counts and proportions of participants at 4-week, 8-week, 12-week, 16-week, and 20-week intervals. These proportions will be accompanied by 95% CIs. The counts and proportions will be accompanied by 2-sided 95% CIs inferred based on binomial distribution for each endpoint and 2-sided 95% simultaneous CIs inferred using the Goodman method (Goodman 1965). The Goodman method is used for obtaining simultaneous CIs for the parameters of a multinomial distribution, for example for a multinomial endpoint (4-week interval, 8-week interval, 12-week interval, 16-week interval, and 20-week interval).

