Sensitivity estimand 2.3 (change in BCVA)	Change in BCVA from Baseline of the extension study at Week 52 and Week 56, i.e., the average difference in BCVA between Baseline of the extension study and the average of Week 52 and Week 56	FAS All data collected until the participant discontinued the study treatment and started alternative treatment(s) will be included.	Analyze on observed data only	Analyze on observed data only	Two-sided 95% CI obtained from MMRM with age categories at the baseline, BCVA categories at the baseline, treatment arm in the core study, and assessment visit as the fixed effect and participant as a random effect

* If the duration of the last interval falls within the following ranges of [q4w, q8w) or [q8w, q12w), [q12w, q16w), [q16w, q20w) or \geq q20w then the floor value of these ranges i.e., q4w, q8w, q12w, q16w, q20w, respectively, will be used for imputation.

** Participants who take prohibited concomitant medication are already excluded from PPS as taking prohibited medication is considered a deviation with impact.

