2.6.3 Handling of missing values/censoring/discontinuations

In case of treatment interruption, if the duration of the last interval falls within the following ranges of [q4w, q8w) or [q8w, q12w), [q12w, q16w), [q16w, q20w) or \geq q20w then the floor value of these ranges i.e., q4w, q8w, q12w, q16w, q20w, respectively, will be used for imputation.

The last potential study treatment may be administered at the Week 52 visit (or at the Week 54 visit for the participants who will have received study treatment at an odd number of inspection visits). Hence throughout this document, analyses based on Week 52 BCVA and other efficacy data are performed if Week 52 data are available. If Week 52 BCVA and other efficacy data are not available, Week 54 BCVA and other efficacy data will be used instead of Week 52. Otherwise, LOCF will be used to impute missing BCVA as per the estimand framework.

For participants who discontinue study treatment but continue in the study, data collected after the switch to alternative treatment in the study eye will be censored for the primary analysis. Censored data will be replaced using LOCF with the last observation collected prior to/on the start of an alternative treatment in the study eye.

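### The minus-4-weeks durability rule puts participants injected for disease activity at a 10- or 14-week inspection visit one category below the interval the protocol assigns them

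*SAP*

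**What the plan says.** **Interval.** SAP 2.1.1: "Treatment interval is defined as the time period from one injection until the next injection". The last interval is the last one with injections at both ends by Week 56.

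**DA rule.** SAP 2.5.2: if DA is present at the end of that interval, "the last interval will be shortened by 4 weeks, down to a minimum of q4w".

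**Rounding.** The footnote to Primary estimand 1 in SAP Table 2-1 takes a length between categories, "then the floor value of these ranges i.e., q4w, q8w, q12w, q16w, q20w, respectively, will be used for imputation". Protocol Table 12-1 has the same footnote: "then the floor value of these ranges i.e. q4w, q8w, q12w, q16w, q20w, respectively, will be used for imputation". Neither limits when it applies. Elsewhere the SAP is narrower. SAP 2.5.2 reads "In case of any treatment interruption or permanent study treatment discontinuation, the imputation techniques as per the estimand framework in" Section 2.5.3 will be considered, and SAP 2.6.3 introduces the same ranges with "In case of treatment interruption, if the duration of the last interval falls within the following ranges".

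**Time scale.** SAP 2.1.1: "All data from scheduled and unscheduled visits will be analyzed based on" the week label in the CRF. It does not say whether interval length is in nominal weeks or actual days.

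**Inspection visits.** Protocol 6.7.2 offers an optional inspection 10 weeks after the last injection (8-to-12 extension), 14 weeks after (12-to-16) and 16 weeks after (16-to-20). The participant is injected there only if DA is seen. After the 10-week inspection: "The next treatment interval will be reduced to 8 weeks". After the 14-week one it is 12 weeks, and after the 16-week one the next treatment is planned 12 weeks later.

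**Minimum.** Protocol 4.1 stops the shortening at 8 weeks. Protocol Table 12-1, 12.4.3 and 12.4.4, and the SAP, stop it at 4.

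**The concern.** Subtracting 4 weeks works when an interval ends at a scheduled 12-, 16- or 20-week visit. Two of the three inspection visits fall 2 weeks off that grid, and an injection there always comes with DA, so the subtraction always applies. The SAP mentions inspection visits only when choosing between Week 52 and Week 54 data; it gives no durability rule for them.

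At stake is the category recorded on a co-primary endpoint for people treated exactly as the protocol directs. The 10-week case also lands in q4w, which protocol 2.1 and SAP 2.5.3 describe as participants assigned to a 4-week interval and taken off study treatment. Protocol 6.7.2 keeps these participants on 8 weeks. The error carries into the secondary last-interval distribution, overall and per core-study arm, and into the change in last interval.

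**Working it through.** **1. The plan's own precision.** Protocol Table 12-3 at N=250, width = 2 × 1.96 × √(p(1−p)/250):

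- q4w, p = 0.086: 6.95% (stated 7%)
- q16w, p = 0.127: 8.25% (stated 8.3%)
- q20w, p = 0.194: 9.80% (stated 9.8%)

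These reproduce and are not in dispute. They serve only as a scale.

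**2. Classification, nominal weeks, DA at the inspection visit.**

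| Extension | Elapsed weeks | Minus 4 | SAP category (round down, minimum 4) | With minimum 8 | Planned interval minus 4 | Next interval, protocol 6.7.2 |
|---|---|---|---|---|---|---|
| 8 to 12 | 10 | 6 | q4w | q8w | 8 | 8 |
| 12 to 16 | 14 | 10 | q8w | q8w | 12 | 12 |
| 16 to 20 | 16 | 12 | q12w | q12w | 16 | 12 |

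Rounding before subtracting gives the same categories: 10 → 8 → 4, 14 → 12 → 8, 16 → 16 → 12. Visit timing hardly matters. Within the ±14-day window, only an inspection exactly 14 days late (12 or 16 elapsed weeks) reaches the protocol's category in the two failing rows.

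**3. If rounding is limited to interruptions.** The 6- and 10-week results then belong to none of the five categories, although treatment followed the protocol.

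**4. When the inspection interval is the last one.** The next planned injection must fall after the last treatment visit (Week 52, or 54 for some).

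- 10-week inspection at week t: t + 8 > 52 (54), so t > 44 (46).
- 14-week inspection at week t: t + 12 > 52 (54), so t > 40 (42).
- Earlier inspections count if treatment then stops.

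Footnote 3 of protocol Table 8-1 foresees an inspection visit with injection at Week 52.

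**5. Size.** Let a and b be the shares of participants in the 10- and 14-week cases. The documents give neither, so the values below are assumptions. Starting from the planned distribution (simulated before the urgent safety measures), recorded q4w = 8.6 + a, q8w = 30.2 − a + b and q12w = 29.2 − b.

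| a = b (assumed) | q4w | q8w | q12w |
|---|---|---|---|
| 1% | 9.6% | 30.2% | 28.2% |
| 2% | 10.6% | 30.2% | 27.2% |
| 5% | 13.6% | 30.2% | 24.2% |

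Half-width for q4w at N=250: 1.96 × √(0.086 × 0.914/250) = 3.48 points, or 8.7 participants, so 9 (3.6%) exceed it. If the true q4w share were 2% (assumption): 1.96 × √(0.02 × 0.98/250) = 1.74 points, or 4.3 participants, so 5 (2%) suffice.

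**6. Time scale.** If actual days were used and the footnote applied to every interval, a 20-week interval closed one day early (139 days, 139/7 = 19.9 weeks) would be recorded as q16w. With nominal weeks this effect is zero.

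**The case against.** **The footnote may not apply.** It speaks of imputation, which the SAP text ties to interruption or discontinuation, and an on-schedule inspection injection is neither. On that reading the category is undefined rather than wrong. This is a fair reading, but it leaves a co-primary outcome without a value, and the footnote attached to the estimand carries no such limit.

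**Planned interval minus 4 would match the protocol at the two disputed visits.** It would, but SAP 2.1.1 defines the interval by injections actually given. This reading also gives 16 weeks at the 16-week inspection, where the protocol gives 12. There it would overstate durability, so the direction of error does depend on the reading.

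**The programming specifications may deal with it.** The SAP refers further programming detail to a separate document, which is not available here. Such a document could add detail, but the SAP already states a rule, and that rule gives the wrong category.

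**The impact is limited.** Inspection visits are optional, the time window is late, and the study is single-arm estimation without a success criterion. Amendment 2 sized it around q20w. On nominal weeks q16w, q20w and the at-least-16-week proportion do not change, and the bias runs against the drug. All of this stands and limits the importance of the point.

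**q4w was already mixed.** A regular 8-week interval ending with DA also becomes q4w under the rule. That stands too: the 10-week case is not the only route by which someone not discontinued could be counted there.

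**Conclusion.** The concern holds. Applied as written, the rule places participants injected for DA at a 10- or 14-week inspection one category below the interval protocol 6.7.2 assigns. Each alternative reading fails in at least one case: limiting the rounding leaves no category, planned-minus-4 fails at 16 weeks, and the 8-week minimum repairs only the 10-week case. Confidence in the classification error is high.

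Its numerical effect is unknown, because the documents give no frequency of inspection injections. The scenario shares are assumptions, and the starting distribution predates the urgent safety measures. The shifts stay within q4w, q8w and q12w and understate durability. This should be fixed, but it does not undermine the long-interval results.

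**What to change.** Before database lock:

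1. When the last interval ends with DA at an inspection visit, classify it by the next interval already assigned in protocol 6.7.2 (8, 12 and 12 weeks for the 10-, 14- and 16-week inspections), not by elapsed weeks minus 4.
2. Classify on-schedule intervals by nominal weeks, and state that the rounding-down rule applies only to interrupted or delayed intervals.
3. Reconcile the 4- and 8-week analysis minima across protocol 4.1, Table 12-1, 12.4.3, 12.4.4 and the SAP.
4. Optionally, add a sensitivity analysis in which a delayed interval ending with DA is not credited beyond the interval that had been planned.

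The cost is SAP wording and derivation programming. Treatment dates, visits and DA assessments are already collected, and items 1 to 3 need no new data or visits.

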For all participants, the last potential study treatment will be at the Week 52 visit. Participants who will receive a study treatment at an inspection visit may have a study visit at Week 54. For those participants, the Week 54 visit will take place in lieu of the visit at Week 52. Hence throughout this document, analyses based on Week 52 BCVA and other efficacy data are performed if Week 52 data are available. If Week 52 BCVA and other efficacy data are not available, Week 54 BCVA and other efficacy data will be used instead of Week 52. Otherwise, LOCF will be used to impute missing BCVA as per the estimand framework.

Table 2-1 Primary and sensitivity estimands

Estimand	Estimand definition	Analysis set, data included in the analyses	Use of data after intercurrent event (missing data imputation techniques)		Statistical methods
			Discontinuation of study treatments	Treatment interruption	
Primary estimand 1 (Duration of last interval with no disease activity)	Duration of the last interval with no disease activity, i.e., distribution of the last interval with no disease activity up to Week 56, i.e., proportion of participants in last interval with no disease activity that is 4/8/12/16/20-weeks intervals	FAS *Last interval with no disease activity up to Week 56.	'While on treatment strategy' will be applied as disease stability assessment will not be performed after the patient discontinued treatment.	Treatment policy strategy will be applied, i.e., include data collected after treatment interruption	Two-sided 95% CI of proportions. If there was disease activity, the last interval will be shortened by 4 weeks, down to a minimum of 4 weeks
Primary estimand 2 (change in BCVA)	Change in BCVA from baseline of the extension study at Week 52 and Week 56, i.e., the average difference in BCVA between baseline of the extension study and the average of Week 52 and Week 56	FAS All data collected until the participant discontinued the study treatment and started alternative treatment(s) will be included.	The hypothetical treatment strategy will be applied, i.e, exclude data collected after study treatment discontinuation, treat them as missing and impute with LOCF	Treatment policy strategy will be applied, i.e., include data collected after treatment interruption	Two-sided 95% CI obtained from ANOVA with baseline age categories, baseline BCVA categories and treatment arm in the core study included as fixed effects

Estimand	Estimand definition	Analysis set, data included in the analyses	Use of data after intercurrent event (missing data imputation techniques)		Statistical methods
			Discontinuation of study treatments	Treatment interruption	
Sensitivity estimand 1.2 (Duration of last interval with no disease activity, and excluding participants with important protocol deviations as per PPS)	Duration of the last interval with no disease activity, i.e., distribution of the last interval with no disease activity up to Week 56, i.e., proportion of participants in last interval with no disease activity that is 4/8/12/16/20-weeks intervals.	PPS** *Last interval with no disease activity up to Week 56.	'While on treatment strategy' will be applied as disease stability assessment will not be performed after the patient discontinued treatment.	Treatment policy strategy will be applied, i.e., include data collected after treatment interruption	Two-sided 95% CI of proportions. If there was disease activity, the last interval will be shortened by 4 weeks, down to a minimum of 4 weeks
Sensitivity estimand 2.2 (change in BCVA, and excluding participants with important protocol deviations as per PPS)	Change in BCVA from Baseline of the extension study at Week 52 and Week 56, i.e., the average difference in BCVA between Baseline of the extension study and the average of Week 52 and Week 56	PPS All data collected until the participant discontinued the study treatment and started alternative treatment(s) will be included.	The hypothetical treatment strategy will be applied, i.e, exclude data collected after study treatment discontinuation, treat them as missing and impute with LOCF	Treatment policy strategy will be applied, i.e., include data collected after treatment interruption	Two-sided 95% CI obtained from ACOVA with baseline age categories, baseline BCVA categories and treatment arm in the core study included as fixed effects

Estimand	Estimand definition	Analysis set, data included in the analyses	Use of data after intercurrent event (missing data imputation techniques)		Statistical methods
			Discontinuation of study treatments	Treatment interruption	
Sensitivity estimand 2.3 (change in BCVA)	Change in BCVA from Baseline of the extension study at Week 52 and Week 56, i.e., the average difference in BCVA between Baseline of the extension study and the average of Week 52 and Week 56	FAS All data collected until the participant discontinued the study treatment and started alternative treatment(s) will be included.	Analyze on observed data only	Analyze on observed data only	Two-sided 95% CI obtained from MMRM with age categories at the baseline, BCVA categories at the baseline, treatment arm in the core study, and assessment visit as the fixed effect and participant as a random effect

* If the duration of the last interval falls within the following ranges of [q4w, q8w) or [q8w, q12w), [q12w, q16w), [q16w, q20w) or \geq q20w then the floor value of these ranges i.e., q4w, q8w, q12w, q16w, q20w, respectively, will be used for imputation.

** Participants who take prohibited concomitant medication are already excluded from PPS as taking prohibited medication is considered a deviation with impact.

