2.2 Secondary estimands

Not applicable

3 Study design

This study is a 56-week, open-label, one-arm extension study in participants who have completed the CRTH258A2303 study (TALON).

[figure not shown]
Participants who consent and meet all the inclusion and none of the exclusion criteria will be enrolled into this extension study and receive brolocizumab 6 mg in a TtC regimen, irrespective of the treatment received in the core study.

Approximately 250 participants from the core study will enter the extension study. The maximum study duration for a participant is 56 weeks, including post-treatment follow-up.

There will be two periods in this study, see [Figure 3-1](#):

- Treat-to-Control treatment period: from Baseline (Day 1) to Week 52
- Post-treatment follow-up period: from Week 52 to Week 56.

Figure 3-1 Study design

Depending on visit schedules:

* 62 weeks (core) / 54 weeks (extension) ** Week 62 (core) / Week 54 (extension)

Baseline visit: Day 1

Participants should sign informed consent no later than the Week 64 (EOS) visit of the core study. Baseline visit for the extension study (extension baseline) should occur on the same day as the Week 64 (EOS) visit of the core study. Participants will be assessed on inclusion and exclusion criteria of the extension study at the baseline visit.

The study eye will be the same eye that received brolucizumab or aflibercept treatment in the core study.

Treat-to-Control treatment period: Day 1 to Week 52

All efforts should be made to adhere to the study visit schedule within a ± 14 day window (baseline visit should occur on the same day as the Week 64 (EOS) visit of the core study). For a given study visit, assessments can be performed on 2 consecutive days provided both days occur within the visit window. Study treatment is intended to be administered on the day of the study visit, or, if this is not possible, within 3 days after the assessments have taken place.

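### The floor rule for the durability co-primary has no stated scope, unit or tolerance; applied as written to days between injections, it drops a within-window gap a full interval category

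*SAP*

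**What the plan says.** The first primary estimand is the distribution of the last interval with no disease activity (DA) up to Week 56 over five categories, q4w to q20w, in the FAS.

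- **Interval.** SAP 2.1.1: "Treatment interval is defined as the time period from one injection until the next injection". SAP 2.5.2 adds that the last interval must have an injection at each end, at or before Week 56.
- **Floor rule, co-primary.** The starred footnote to SAP Table 2-1 reads "If the duration of the last interval falls within the following ranges of [q4w, q8w) or [q8w, q12w), [q12w, q16w), [q16w, q20w", with an open top bin from 20 weeks. The lower end of the bin "will be used for imputation". Protocol Table 12-1 carries the same footnote ("If the duration of the last interval falls within the following ranges of [q4w, q8w"). Neither version states a tolerance or a restriction to particular participants. The PPS version of the estimand carries the same star.
- **Floor rule, SAP 2.6.3.** The same bins are introduced by "In case of treatment interruption, if the duration of the last interval falls within the following ranges".
- **Cross-reference.** SAP 2.5.2 sends the reader to the techniques of Section 2.5.3 for treatment interruption or permanent discontinuation.
- **Visit timing.** Protocol Section 3: "All efforts should be made to adhere to the study visit schedule within a ± 14 day window". Injection is meant for the visit day "or, if this is not possible, within 3 days after the assessments have taken place".
- **Visit labels.** SAP 2.1.1 ends by saying that visit data are analysed by the week recorded in the CRF unless otherwise stated.

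**The concern.** The bins are closed on the left at exactly 4, 8, 12, 16 and 20 weeks. Real gaps between injections scatter around those values, and the Protocol allows that scatter. If the gap is measured in days, every shortfall, however small, crosses a boundary, and no permitted overrun does. The error then runs only towards shorter intervals.

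This bears on a co-primary endpoint. The rationale for Amendment 2 re-assessed the sample size around estimating the q20w proportion. A bias from scheduling would not shrink with sample size and would not show in the confidence interval. The PPS sensitivity analysis uses the same footnote, so it would not reveal the problem. At the lower end, a q8w participant would be counted as q4w, the category for which Protocol 9.1.1 requires study treatment to stop.

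**Working it through.** **1. The plan's own precision figure.** Protocol 12.8 gives a q20w proportion of 19.4% with a 95% CI width of 9.8% at N=250. Wald width: 2 × 1.96 × √(0.194 × 0.806 / 250) = 3.92 × 0.0250 = 9.8%. This reproduces the figure; the half-width is 4.9 points.

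**2. Coding on an actual-day reading.** Planned days = 7 × weeks, binned as in the footnote.

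| Planned | Target day | 1 day short | 14 days short | 14 days long |
|---|---|---|---|---|
| q20w | 140 | 139 → q16w | 126 → q16w | 154 → q20w |
| q16w | 112 | 111 → q12w | 98 → q12w | 126 → q16w |
| q12w | 84 | 83 → q8w | 70 → q8w | 98 → q12w |
| q8w | 56 | 55 → q4w | 42 → q4w | 70 → q8w |

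A long gap moves up a category only at +28 days. If DA is present at day 139, the result is q12w whether flooring or shortening comes first (139 → q16w → q12w, or 139 − 28 = 111 → q12w). The planned category less 4 weeks would be q16w.

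**3. What counts is the gap.** Two injections with equal offsets leave the gap unchanged. A late opening injection followed by an on-schedule closing one shortens it.

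**4. Size.** Let e be the share of last intervals that are short. The documents do not give e, so it is assumed. The inputs are the planning proportions in Protocol Table 12-2 (8.6, 30.2, 29.2, 12.7 and 19.4%), which predate the urgent safety measures. Then q20w = 19.4(1 − e); q4w = 8.6 + 30.2e; at least 16 weeks = 19.4 + 12.7(1 − e).

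| e | q20w | Loss (points) | q4w | ≥16 weeks |
|---|---|---|---|---|
| 0 | 19.4% | 0 | 8.6% | 32.1% |
| 10% | 17.46% | 1.94 | 11.62% | 30.83% |
| 25% | 14.55% | 4.85 | 16.15% | 28.93% |
| 45% | 10.67% | 8.73 | 22.19% | 26.39% |

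The q20w loss equals the half-width at e = 4.9/19.4 = 25%. As a guide to e, simulated symmetric normal offsets at both injections, rounded to days and clipped at ±14, with an assumed SD of 1 to 7 days, make 36% to 48% of gaps short. If only the closing injection varies, the range is 31% to 47%.

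**5. Other readings.** In nominal CRF weeks, a visit one day early keeps its planned week and the bias is 0. If the floor applies only to interruption, only participants with an interruption are affected.

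**6. Inspection visits with DA.** These give planned gaps of 10, 14 and 16 weeks. No single shortening rule agrees with Protocol 6.7.2 at all three:

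| Injection at | Floor, then −4 | Planned interval, then −4 | Next interval in Protocol 6.7.2 |
|---|---|---|---|
| 10 weeks (planned 12) | q4w | q8w | 8 weeks |
| 14 weeks (planned 16) | q8w | q12w | 12 weeks |
| 16 weeks (planned 20) | q12w | q16w | 12 weeks |

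**The case against.** A reader might infer that compliant participants will be miscoded. The documents do not establish that, for four reasons.

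- **Unit.** No passage says actual days. Intervals are described in weeks, the worked examples in SAP 2.1.1 and Protocol 6.7.2 are nominal, and SAP 2.1.1 analyses visit data by CRF week. The bins have a use on that reading too, because inspection-visit injections create 10- and 14-week intervals.
- **Scope.** The footnote sits in a section on missing values and discontinuations and calls itself imputation. SAP 2.5.2 invokes that section for interruption or discontinuation, and 2.6.3 states the rule for interruption alone. Section 2.6.3 is not purely about secondary endpoints, since it also mentions the primary analysis.
- **Size.** Every non-zero figure above rests on an assumed share and on the actual-day reading.
- **Context.** The study has one arm and estimates without a hypothesis test, and the unseen programming specifications may settle the derivation.

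All four stand, and they limit the finding without removing it. The CRF-week rule concerns visit data, whereas intervals are defined by injections, which may follow the visit by up to 3 days. The footnote carries no interruption limit in either document, so the SAP states one rule with two scopes. Two programmers could follow it and report different co-primary distributions.

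A further inference, that a 4-week interval closed at day 27 would fall in no bin, should also be dropped. Participants needing q4w are excluded at entry or discontinued, so no closing injection is expected. A coded q4w should come from DA shortening of q8w.

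**Conclusion.** The co-primary derivation is ambiguous in scope and unit. On one natural reading it is biased towards shorter intervals. On that reading, a gap 1 to 14 days short of plan loses one category and a gap up to 14 days long gains none. The planned 19.4% at q20w would be reported as 17.5%, 14.6% or 10.7% if 10%, 25% or 45% of gaps were short. The bias is zero on nominal weeks and is confined to interrupted participants if the floor has that scope.

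The documents do not decide between these readings, so they do not support the stronger statement that the reported distribution will be wrong. The point should be fixed before database lock. Confidence is moderate: the wording and arithmetic are clear, but how the rule will be programmed is not known.

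**What to change.** In SAP 2.5.2 and the Table 2-1 footnote:

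1. Limit the floor to intervals affected by treatment interruption, in line with 2.6.3, and state the unit of duration.
2. Classify all other DA-free scheduled intervals by the planned interval when the gap between injections is within 14 days of it. Take the planned interval from IRT if it is stored there, otherwise from nominal CRF weeks. Give a rule for ties (126 days is 14 from both 112 and 140) and for gaps outside the tolerance.
3. Apply the 4-week DA shortening to that planned category at scheduled treatment visits only.
4. State a separate coding rule for injections at inspection visits (10, 14 and 16 weeks), reconciled with Protocol 6.7.2.

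The cost is SAP wording and a short set of derivation rules before lock. The Protocol says that IRT registers visits, dispensing and DA assessments. It does not say that IRT stores the planned interval, so that needs checking first.
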